5.3. Data Banking for Future Research Use

Data will be stored in a password protected file on a password protected computer in the research coordinator's office. They may be used in future studies. Data will be de-identified to protect participants' privacy and then coded accordingly. Only the research investigators in this protocol will have access to the data. Each file will also be saved with password protection. The data will be stored for 7 years. Participants will not be re-contacted regarding the stored data.

5.4. Genetic/Genomic Research Activities

There will not be any genetic and genomic research activities either as the primary objective of the study or as an ancillary activity.

5.5. Costs to the Subject

There will be no cost to the subjects for the DIAL-SDM visits.

5.6. Payment for Participation

Each patient will be paid up to a total of \$100. This amount will defray participant travel costs while providing a small incentive without coercion. To protect the participant's right to withdraw without penalty, payment will be prorated as the following: completion of first set of data collection, \$50; Final set, \$50. Participants who withdraw from the study and voluntarily complete an exit interview will receive payment of \$10.

Each caregivers will receive \$50 for each set of surveys, for a maximum of up to \$100.

All payment to subjects and caregivers will be made with a gift card that for each visit will be uploaded with their \$50 payment. These gift cards have no value until the department has been

made aware by the researcher that the gift cards have been given to the subjects and not lost or stolen. This process will be through the Embark system which will ensure the safety of the researcher who is distributing payment.

Each physician will receive a \$100 gift card upon the completion of the study.

Each patient coach will receive a \$50 gift card upon completion of the qualitative interview.

Each physician coach will receive a \$50 gift card upon completion of the qualitative interview.

Each research coordinator will receive a \$50 gift card upon completion of the qualitative interview.

6. CONCOMITANT AND DISALLOWED MEDICATION

There is no concomitant or disallowed medications in this study.

7. SUBJECT WITHDRAWALS

Participants will be advised that they have the right to withdraw from the study at any time without prejudice. Participants may also be withdrawn from the research without their consent in the event of acute worsening of their kidney disease needing initiation of hemodialysis before completion of the study. If a caregiver withdraws from the study, another caregiver identified by the patient will be approached. All participants who withdraw from the study will be offered an exit interview.

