patients, caregivers and nephrologists will be interviewed by the RA after the last meeting with the nephrologist to assess the feasibility and acceptability of the DIAL-SDM intervention. For patients in the intervention arm, the interviewer will ask open-ended questions on (1) benefits of the intervention (2) barriers to accessing DIAL-SDM (3) usefulness of the dialysis options knowledge materials (4) dialysis decision making. Interviews will be audio recorded. Similarly, patients in the control group will be asked about (1) the process of dialysis decision-making (2) experience of communicating goals and preferences with their nephrologist and if their goals were discussed during the visits with their nephrologist. Patients who decide to withdraw from the study will be interviewed when the individual confirms their withdrawal and will be asked (1) main reason for withdraw (2) suggestions for improving the study. These interviews will either take place at Strong Hospital or a location of patient's choice (ex: patient's home).

Medical Records Abstraction: We plan to record patients' labs, co-morbid conditions, advanced care planning, hospitalizations and ER visits for a total of 6 months before and 6 months after study entry on an abstraction form. This retrospective abstraction will be performed only for participants who have already enrolled and completed the study; no new patients will be recruited or consented for this purpose.

Because this is a retrospective study that involves retrospective chart review, we will also look at patient mortality, place of death, receipt of hospice services, receipt of aggressive procedures such as CPR, dialysis etc. and long-term healthcare utilization for both the control and intervention groups within 3 years of the subjects study completion date without patient consent.

Because this study involves only participants who are already enrolled and poses minimal risk, we are requesting approval to obtain HIPAA authorization verbally using a short script. This approach reduces burden for participants who have already completed study activities, while ensuring they are informed about the additional retrospective chart review.

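### Optional withdrawal at acute hemodialysis start, and chart follow-up tied to study completion, select patients on post-randomisation events in the chart and completion-time choice comparisons

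*Combined protocol and SAP*

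**What the plan says.** Section 7 (Subject Withdrawals) gives the study the option of having a participant "withdrawn from the research without their consent in the event of acute worsening of their kidney disease needing initiation of hemodialysis", if this happens ahead of study completion. The only data collection it attaches to withdrawal is this: "All participants who withdraw from the study will be offered an exit interview". Table 6 lists that interview as three items.

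Section 5.2 (Medical Records Abstraction) describes two chart reviews.

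- The first covers labs, comorbidities, advance care planning, hospitalizations and ER visits "for a total of 6 months before and 6 months after study entry". Its population is explicit: "This retrospective abstraction will be performed only for participants who have already enrolled and completed the study".
- The second is longer: "we will also look at patient mortality, place of death, receipt of hospice services", together with aggressive procedures (CPR and dialysis are named) and long-term utilisation, in both arms, "within 3 years of the subjects study completion date without patient consent".

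The next paragraph says "we are requesting approval to obtain HIPAA authorization verbally using a short script", and describes the people concerned as having already finished their study activities. Section 5.1 separately lists access to medical records among the things for which patients give written permission.

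Aim 2(c) in Section 1.1 is the patient's initial choice among home dialysis, in-center dialysis and conservative management, at entry and completion. Table 6 also records it at 0-3 months. Table 4 admits only patients who have not yet decided about dialysis.

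Sections 8.2 to 8.4 class death and inpatient hospitalization as serious adverse events and log them from consent. Section 8.3 ends the recording of adverse events at completion or withdrawal.

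**The concern.** Inclusion in the chart reviews depends on reaching study completion, and completion can be cut short by death or by an acute start of hemodialysis. Death and dialysis are themselves outcomes of the longer review. Both occur after randomisation. The intervention addresses the choice between dialysis and conservative management, so the share of patients lost this way may differ by arm.

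Dialysis start is foreseeable here. Table 4 requires a GFR of 25 ml/min or below, and Section 4.1 lets nephrologists decline patients unlikely to progress to dialysis. The withdrawal rule is discretionary, the protocol does not say who applies it, and coached nephrologists know their assignment.

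At stake are the between-arm comparison of chart outcomes and, to a lesser extent, Aim 2(c). Aim 2 exists to produce effect sizes for a larger trial (Sections 1.1, 2.2 and 3.1), so a selected estimate and the rule that produced it could both carry forward.

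**Working it through.** **The plan's one computed figure.** Section 3.1 claims 80% power for a 15-point OPTION difference (SD 11, ICC 0.1, cluster-size CV 0.5, 60 patients). Section 9.1 gives about 12 nephrologists, so 60/12 = 5 patients each. I assume 30 patients per arm.

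- Design effect = 1 + [(1 + 0.5²) × 5 − 1] × 0.1 = 1.525; effective n per arm = 30/1.525 = 19.7.
- Power is 99.0% (normal) or 97.0% (noncentral t, 10 df), so the stated 80% is not reproduced but is conservative.
- If 12 of the 60 are lost (48 left, 4 per cluster), the design effect is 1.40, effective n is 24/1.40 = 17.1, and power is 94.8% (t).

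Loss of numbers is therefore not the issue for OPTION. The issue is who is lost.

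**Who is counted where.**

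| Patient | 6-month abstraction | 3-year review | Adverse event log |
|---|---|---|---|
| Completes | Yes | Yes | To completion |
| Dies on study | No (explicit) | No completion date to start from (implied) | Death logged |
| Withdrawn at acute hemodialysis start | No (explicit) | No completion date to start from (implied) | Open events followed until resolved or stable; new ones not recorded |

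No text links the log to the chart outcomes.

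**Size of the selection.** Let p be the risk among all enrolled patients in an arm, w the share lost before completion, and r the risk among those lost. The risk among completers is (p − w·r)/(1 − w). This ignores the shift in the follow-up window. All values of p, w and r are assumptions, because the documents give none.

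3-year mortality, p = 40% in both arms (true difference 0):

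| Loss, arm A / arm B | r | Completers, A / B | False difference |
|---|---|---|---|
| 5% / 20% | 60% | 38.9% / 35.0% | 3.9 points |
| 5% / 20% | 100% | 36.8% / 25.0% | 11.8 points |
| 10% / 30% | 60% | 37.8% / 31.4% | 6.3 points |
| 10% / 30% | 100% | 33.3% / 14.3% | 19.0 points |

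First row: (0.40 − 0.05 × 0.6)/0.95 = 0.389 and (0.40 − 0.20 × 0.6)/0.80 = 0.350.

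If w and r are equal across arms, the observed difference is (p_A − p_B)/(1 − w). That is zero when the true difference is zero; a real difference is stretched by 1/(1 − w). The level is still understated: 38.9% at w = 5%, r = 60%, down to 25.0% at w = 20%, r = 100%, instead of 40%. Equal loss alone is not enough: with w = 10% in both arms and r = 60% against 100%, completers show 37.8% against 33.3%, a false 4.4 points.

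Completion-time choice, taking p = 50% in-center in both arms, every lost patient in-center, and none with a usable later survey (the extreme case):

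- 5% / 20% lost: 0.45/0.95 = 47.4% against 0.30/0.80 = 37.5%, a false 9.9 points.
- 10% / 30% lost: 0.40/0.90 = 44.4% against 0.20/0.70 = 28.6%, a false 15.9 points.

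**The case against.** Much can be said for the plan.

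- **The withdrawal rule is narrow.** A reader might infer that any hemodialysis start removes a patient automatically. Section 7 says only that patients may be withdrawn, and only for acute worsening.
- **Aim 2(c) is choice, not receipt.** An emergency start need not be the patient's choice, and a patient withdrawn after the 0-3 month survey keeps a post-visit value. The choice illustration is therefore an upper-end case.
- **Deaths on study are recorded.** A reader might infer that every death before completion vanishes. The serious adverse event log captures a death in a patient not already withdrawn. The gap is that nothing carries the log into the chart outcomes, and recording stops at withdrawal.
- **The completer limit on the 3-year review is inferred.** It is explicit for the 6-month abstraction only. For the longer review it rests on the completion-date origin and the description of participants as having finished study activities.
- **There is a missing-data plan.** Section 11.1 offers inverse probability weighting, multiple imputation and sensitivity analyses if necessary. That may help with missing choice data. It cannot recover charts never abstracted, and a patient who died before completion is missing because of the outcome itself, which the missing-at-random assumption does not cover.
- **The shifts are modest beside sampling error.** With 30 per arm and a proportion near 50%, the standard error of a difference is √(2 × 0.25/30) = 12.9 points before clustering. But bias does not shrink with sample size, and these estimates are meant to inform a larger trial.

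It might also be inferred that deceased patients must drop out of the review because they cannot give verbal authorization. The documents do not say how decedents would be handled, and written record-access permission already exists. What stands is that the authorization statements conflict.

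**Conclusion.** The concern holds in limited form. As written, the 6-month chart comparison is restricted to completers, and the 3-year comparison is restricted by implication. Completion-time choice is missing for withdrawn patients with no later survey. This is selection on post-randomisation events related to the outcomes, and the rule leaves room for it to differ by arm.

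Its size cannot be stated. Under the assumed losses the false mortality difference runs from about 4 to 19 points, and its sign depends on which arm loses more. With no true difference, it is zero if loss and risk among those lost are equal across arms.

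A reader might conclude that the trial's main result is compromised. The documents do not support that. The primary aim is feasibility, acceptability and fidelity; mortality, hospice and CPR appear in no listed aim; and Section 11.1 names no analysis of them. The point is worth correcting because it is cheap to correct, but it is not a condition for the study's validity.

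**What to change.** 1. **Section 7.** State that a patient who starts hemodialysis stays in the assigned arm for data collection. Take modality and start date from the chart, and seek the remaining surveys where the patient agrees. This concerns data only; clinical care and coaching stay with the clinical team.
2. **Section 5.2, population.** Abstract charts for all enrolled patients, including those who died or left early, except those who withdraw permission for record use.
3. **Section 5.2, time origin.** Start the 3-year review at study entry, as the 6-month window already does, and bring in pre-completion deaths from the serious adverse event log. Entry is also the cleaner origin because completion is timed from the nephrology visits, which vary between patients.
4. **Section 5.2, authorization.** Reconcile the statement that no patient consent is needed, the verbal HIPAA authorization, and the written record-access permission in Section 5.1. Put one basis to the IRB that also addresses decedents.

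The cost is protocol and IRB wording plus a few more charts. Under the loss rates assumed above, with 30 per arm, that is 30 × (0.05 + 0.20) = 7.5 to 30 × (0.10 + 0.30) = 12 patients. Because the review is retrospective, the information may still be recoverable.

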8. SAFETY AND REPORTABLE EVENTS

8.1. Adverse Event Definition

An adverse event is any symptom, sign, illness, or experience which develops or worsens during the study, whether or not the event is considered related to study.

8.2. Serious Adverse Event

A serious adverse event is defined as any adverse medical experience that results in any of the following outcomes:

- Death
- is life-threatening
- requires inpatient hospitalization or prolongation of existing hospitalization
- Results in persistent or significant disability/incapacity, or
- requires medical or surgical intervention to prevent permanent impairment or damage.

8.3. Recording Adverse Events

At each visit, patients will have the opportunity to report any adverse events by reporting all voluntary complaints of the participant.

All adverse events will be documented. Each adverse event will include a brief description of the experience, the date of onset, the date of resolution, the duration and type of experience, the severity, the relationship to study and contributing factors.

The recording of adverse events will occur once the participant signs consent until subject completes the study or withdraws from participation. The adverse experience will be followed until the adverse event is resolved or stabilized.

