that a combination of their demographic data will be used as their passcode. The study coordinator will use the combination of the subject's date of birth, and street name as variables to represent the verification passcode which the subject/subject's legally authorized representative will be prompted to answer when accessing the eConsent link. Subjects will have the capability to sign electronically with a stylus, mouse or finger. Once the consent form is signed and submitted, subjects will be able to receive a print out of the paper copy, download a PDF, and/or receive an email with a PDF attachment of the signed consent form. If a signed copy of the consent will be emailed to the subject using REDCap, the subjects will provide their email address on the completion page, the following statement will be included in the field where the email address will be provided:

Enter your email to receive confirmation message? A confirmation email will be sent to all respondents that have completed the survey, but because your email address is not on file, the confirmation email cannot be sent automatically. If you wish to receive it, please enter your email address below.

Documentation of how consent was obtained will be kept in the subject files to ensure an accurate representation of the consent process used to obtain consent with each subject. Patients in both Intervention and Usual Care arm will receive nephrology visit documentation as per clinical standards. Visits with coach will not be documented in the patient's electronic medical record but on separate forms. Also, dialysis education for Usual Care arm is routinely not documented in patient's electronic medical record.

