Approximately, 2-4 weeks prior to the visit with a coach, patients will receive an educational booklet about renal replacement therapy options and conservative management and another booklet containing a list of most commonly asked questions. Educational booklet will also be sent in a video format. Participants in the intervention group will then meet with a coach for approximately 60-90 minutes within two weeks prior to an office visit with their nephrologist. This intervention can take place at the Strong Hospital site or an alternate location of the patient's choice. If intervention takes place at the subject's home, a room that ensures privacy and confidentiality will be requested for the process to take place. Also, if at subject's home, study activities that are being conducted will use the same methods as if on site at URM. During the first half of the coaching session, the coach will administer the value affirmation exercise, identify goals/preferences of kidney disease treatment so that they can articulate to the nephrologist and review renal replacement therapy options including conservative management with the patient. The coach will not answer any questions regarding RRT options but would rather help patients formulate questions about different RRT options including conservative management. Subsequently, the coach will give each patient (and caregiver) a list of commonly asked questions ("question prompt list" or QPL), and use brief role-plays to identify and help prepare patients to ask personally relevant questions during their upcoming nephrologist visit, so they can participate more actively and assertively in discussions with their nephrologist. If a patient has not read the education material or QPL, they will be given an opportunity to read the material or watch the video. Patient's questions along with renal and overall prognosis, using standardized tools (Schmidt RJ, Landry DL, Cohen L, et al. Derivation and validation of a prognostic model to predict mortality in patients with advanced chronic kidney disease. *Nephrology Dialysis Transplantation*. 2019;34(9):1517-1525. doi:10.1093/ndt/gfy305) (Tangri N, Stevens LA, Griffith J, et al. A predictive model for progression of chronic kidney disease to kidney failure. *JAMA - Journal of the American Medical Association*. 2011;305(15):1553-1559. doi:10.1001/jama.2011.451) will be forwarded to the nephrologist a day before the visit, either in-person or via e-mail. Patients (as well as the research coordinator) will also bring a list of their questions and visit checklist to the nephrologist. The nephrology visit will be audio recorded and the recordings will be destroyed after transcription and analyzation is complete. The coach will make a follow-up telephone call

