
(after the nephrology office visit) to address patients' concerns. Patients (and caregivers) will be eligible to attend an additional coaching session if unable to make a decision about dialysis with their nephrologist in one session. A manual and fidelity checklist will be developed to deliver this component of the intervention. Patients will be able to participate in these sessions via zoom or in-person at Strong Hospital or an alternate location chosen by the patient (ex. patient's home).

*If the research coordinator or coach will be traveling to a subject's home, in order to ensure their safety, travel to homes will only take place during daylight hours. They will also ensure that there is another team member who knows where and when they are traveling. The research coordinator or coach will also know to cut the study visit short if or when necessary and that they will have means of communication with the PI by cell phone or 911 in the case of an emergency.

In addition, no mandated reporters will be entering the subjects home at any time but if there are any problematic behaviors observed in the home, the study team member witnessing the incident will report/discuss with the PI and, if necessary, the IRB.

Control Group patients (and caregivers, if available): will meet with the dialysis educator and their nephrologist, as per the standard clinic protocol, and complete three sets of assessments. Their first set of assessments will be done at study entry, the second set will be completed within 0-3 months of seeing their nephrologist and a decision has been finalized (spanning up to two visits), and their third set will be completed at study completion which will take place within 3-6 months after their nephrology visit.

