8.4. Responsibilities for Reporting Serious Adverse Events

The investigator will record all serious adverse experiences that occur during the study period in an Adverse Event log. The study period for reporting serious adverse events starts from the

time of signing consent to the final study visit. The PI will be notified of all adverse events. The Investigator will comply with regulations and RSRB policy regarding the reporting of adverse events.

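### Section 8.3 relies on patients' voluntary complaints at undefined visits to find non-serious adverse events, and gives no step for asking caregivers

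*Combined protocol and SAP*

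**What the plan says.** Section 8.1 defines an adverse event broadly, as "any symptom, sign, illness, or experience which develops or worsens during the study, whether or not the event is considered related to study". Section 8.3 undertakes to document all of them, from consent until completion or withdrawal. Its only step for finding them is: "At each visit, patients will have the opportunity to report any adverse events by reporting all voluntary complaints of the participant". For each event it asks for a description, onset and resolution dates, and "the duration and type of experience, the severity, the relationship to study and contributing factors".

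Serious events have their own rule in 8.4: "The investigator will record all serious adverse experiences that occur during the study period in an Adverse Event log". The same section has the principal investigator notified of all adverse events.

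The contacts are set out in 5.1 and 5.2. Both arms have three survey sets and one or two audio-recorded nephrology visits. In addition, "Participants in the intervention group will then meet with a coach for approximately 60-90 minutes within two weeks prior to an office visit", and the coach telephones after that visit about the patient's concerns. A second coaching session is offered if no dialysis decision has been reached. Control patients meet a dialysis educator under the clinic's usual protocol. On records, 4.2 says: "Visits with coach will not be documented in the patient's electronic medical record but on separate forms". It also says that "dialysis education for Usual Care arm is routinely not documented in" the patient's electronic record.

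Caregivers give their own consent (4.2). Section 9.1 names both patients and caregivers as at risk of minor psychological discomfort.

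**The concern.** A broad definition is paired with passive capture. An event that nobody asks about is recorded only if the patient volunteers it, at a contact that someone treats as a visit. The harm that 9.1 foresees is discomfort from talking about illness and prognosis. That is subjective and usually non-serious, so voluntary reporting can miss it.

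Caregivers fall within the 8.3 recording period once they consent, but the sentence on how events are found mentions patients only.

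What is at stake is how the non-serious part of the log can be read. The safety board confers when adverse events occur and advises on early termination (11.2), and the pilot is meant to lead to a larger trial (2.2). A short list of non-serious events could mean few events or few questions, and the plan does not let a reader tell which.

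**Working it through.** The plan gives no adverse-event rate or target, so there is no figure to reproduce. The check compares the relevant sections and then counts contacts.

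**1. Is a question asked anywhere?** Tables 6 and 7 list no adverse-event item. The nearest is the two-item hospitalization measure for patients in Table 6, which has no counterpart in Table 7. The interview topics in 5.2 cover benefits, barriers, materials and decision-making (intervention), and decision-making and communication of goals (control). The exit interview covers the reason for leaving and suggestions. None asks about harm. Section 5.2 places the questionnaires in an appendix that was not supplied, so an item inside one of them cannot be ruled out.

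**2. What else could pick up events?**

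| Source | Who is covered | What it picks up | Stated to feed the adverse-event record? |
|---|---|---|---|
| 8.4 | All subjects | Serious events | Yes |
| 9.2 distress monitoring | Patients and caregivers | Visible distress, with response and referral | No |
| 11.2(b) board review | Participants in distress | Psychiatric referrals and their outcomes | No |
| 5.2 chart abstraction | Patients who completed the study | Hospitalizations and ER visits, 6 months either side of entry | No |
| Table 6 hospitalization item | Patients | Hospitalizations | No |

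**3. Do the arms have equal chances to report?** The counts below are per patient and use the contacts in 5.1 and 5.2. The end-of-study interview is left out because it adds one to each arm.

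- *Only survey sets and nephrology visits count.* With one nephrology visit each, 3 + 1 = 4 in both arms. With two each, 3 + 2 = 5 in both. There is no excess.
- *Coaching sessions and coach calls also count; the educator does not.* With one nephrology visit, 3 + 1 + 1 + 1 = 6 coached against 3 + 1 = 4 control. With two nephrology visits, two sessions and two calls (a second call is an assumption), 3 + 2 + 2 + 2 = 9 against 3 + 2 = 5. Coached patients have more.
- *Coaching sessions and the educator meeting count; calls do not.* With one nephrology visit each, 3 + 1 + 1 = 5 in both arms. If the control patient needs two nephrology visits and the coached patient one, 3 + 1 + 1 = 5 coached against 3 + 2 + 1 = 6 control. Control patients have more.

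These are counting rules, not reporting rates. Each fits the text, and together they give no excess, an excess in the coached arm and an excess in the control arm.

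**4. How many caregivers are involved?** Section 3.1 expects 60 patients and 36 caregivers: 36 / (60 + 36) = 36 / 96 = 37.5%.

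**The case against.** The strongest reply is that this is a low-risk behavioural pilot whose main foreseeable harm is already watched for. Under 9.2, research assistants look for distress in patients and caregivers and act on it, and the board reviews referrals. Section 8.3 undertakes to document all adverse events, with onset, severity, relationship and contributing factors, and the principal investigator is told of them all. Chart abstraction gives a record of hospitalizations and ER visits that does not depend on coach contact, and some ER visits may be non-serious. Section 11.1 plans no comparison of adverse events by arm.

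Most of this stands, and it keeps the point minor. It would be wrong to say that caregivers have no safety step. But apart from 8.4 none of these sources is stated to feed the adverse-event record. Chart abstraction covers patients who completed the study, so it misses caregivers and those who withdrew. The descriptive fields apply only to events that someone voiced.

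A reader might also infer that the design biases non-serious event counts upward in the coached arm. The documents do not support that. No route to the log is stated for coach contacts, just as none is stated for the educator; coach visits are said only to be kept on separate forms. The coach call is described in the context of decision support: 5.1 also uses it to learn whether a decision was reached. Coaches are study staff, so a route is plausible, but it would have to be assumed.

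**Conclusion.** The point holds as a minor gap in safety capture. Section 8.3 finds non-serious events only through patients' voluntary complaints at undefined visits, and gives no step for asking caregivers, an expected 37.5% of patients plus caregivers.

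No size or direction can be given for a difference between arms. If coaching sessions and calls count as visits, coached patients may have more chances to report. If only the shared nephrology visits and surveys count, and the number of nephrology visits is equal, they do not. No planned analysis is affected, and serious events are outside the point because 8.4 covers them.

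The conclusion assumes that the unsupplied questionnaires contain no adverse-event item. If one does, the same way in both arms and for caregivers, what remains is to define visit and to link that item to the record.

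**What to change.** In 8.3:

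- Keep capture at each visit, and state which contacts are visits.
- Add one scripted adverse-event and distress question, asked by the research assistant of every patient (or the representative who completes the assessments) and every caregiver, in both arms. Ask it at the existing 0-3 and 3-6 month survey sets, covering the time since consent or since the last set, and at the exit interview for those who withdraw. Everyone who completes both sets then has two identical prompts, whichever arm they are in.
- Record the source of each event: scripted question, coach, nephrology visit, or other (including distress seen under 9.2).
- Base any description by arm on the events found through the common question. Show coach-reported events on a separate line and do not drop them.
- Check the Table 6 hospitalization item and the chart abstraction against the 8.4 log, for the time from consent to the final study visit.

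This needs protocol wording and one question at contacts that already take place, with no new visits or staff. The cost is a minute or two per survey and a longer event list to review.
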